##### 5.4.4.1 *Sample Size Determination*

As a pilot study, the data obtained will provide information necessary for a formal sample size estimate for a subsequent larger study. A sample size of 20 patients is estimated to be sufficient to provide a 95% confidence interval of +/- 15 minutes around mean procedure duration, assuming a procedure duration of 95 minutes with a standard deviation of 20 minutes.

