**Sample Size:**

Up to 20 participants will be enrolled in the study.

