## 4 STUDY PROTOCOL

### 4.1 Study Design

This study is a prospective, pilot study using the Attune Medical ensoETM esophageal heat transfer device to actively cool the esophagus during RF ablation procedures. This design is appropriate to gather the data needed regarding overall procedural time, compare this to historical controls, and estimate a sample size for a larger study powered for statistical significance.

Once patient consent is obtained, the subject will undergo preparation and anesthesia procedures following standard practice. Once the patient is intubated, the esophageal heat transfer device will be placed into the esophagus according to the IFU. The device will remain in place until the ablation procedure is completed and will be removed before extubation. Posterior left atrial wall ablation using standard parameters will only be performed when the ensoETM has reached a temperature of 4-6°C for at least 2 minutes. The device will be set to neutral or warming temperature (37-42°C) during other aspects of the procedure (such as mapping and anterior wall ablations).

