#### 5.4.1 Case Report Forms

The Center will perform primary data collection based on source-documented hospital chart reviews and data transcribed or exported from the mapping and navigation system. Temperature set point and timing will be transcribed and annotated into the mapping software.

Deviations from the study protocol or adverse events will be recorded on the appropriate forms (Deviation / Adverse Event Report). Deviations will be documented, and patients will be excluded from

---

final analysis although deviations will be documented and summarized in final reports. Any deviations that concern patient safety and/or the rights of a study subject will be reported to IRB within 24 hours.

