#### 5.4.3 Protocol Deviations and Modifications

Any changes to the approved clinical study must originate from Sponsor in the form of a protocol amendment that must be submitted to the relevant IRB contact. Protocol deviations should be avoided by the PI and site supporting staff. Any deviation from the protocol should be reported to the Sponsor. Any deviation to the clinical study will be reported to the ethical committee in accordance with local requirements. In the situation where deviating from the protocol is in order to protect the life or physical wellbeing of the subjects, which are considered emergency deviations, these should be reported to the Sponsor and Ethical Committee per their local guidelines.

A deviation is any variance from the Investigational Plan requirements (e.g., failure to obtain informed consent, failure to meet inclusion/ exclusion, etc.).

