## **Evaluable Population**

All enrolled subjects who have received catheter ablation of persistent and paroxysmal atrial fibrillation with complete ablation data and procedural timing will be included in the evaluable population.

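### The planned precision of ±15 minutes does not follow from its own inputs: 20 patients with an SD of 20 minutes give about ±9.4, and the gap is not explained

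*Combined protocol and SAP*

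**What the plan says.** The sample size paragraph (section 5.4.4.1) describes 20 patients as "sufficient to provide a 95% confidence interval of +/- 15 minutes around mean procedure duration". The inputs behind that figure appear at the end of the same sentence: "assuming a procedure duration of 95 minutes with a standard deviation of 20 minutes". It shows no formula and mentions no attrition, assurance probability or allowance for uncertainty in the SD.

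These other parts of the document bear on the number:

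- The synopsis makes 20 a ceiling: "Up to 20 participants will be enrolled in the study".
- Section 4.1 says that one purpose of the pilot is to "estimate a sample size for a larger study powered for statistical significance".
- Section 5.4.1 removes patients with deviations from the final analysis ("Deviations will be documented, and patients will be excluded from" it), and section 5.4.3 defines the term broadly: "A deviation is any variance from the Investigational Plan requirements".
- Section 5.4.4.2 admits only subjects "with complete ablation data and procedural timing will be included in the evaluable population".

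None of these gives an expected loss or refers back to the sample size.

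**The concern.** A confidence interval for a single mean is fixed by the number of patients, the SD and the confidence level. Section 5.4.4.1 states all three and then a half-width that they do not produce. Sections 3.2 and 4.1 explain why a pilot is being run, but only section 5.4.4.1 attaches a calculation to the 20 patients.

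Two things are at stake, both modest. First, an ethics committee or reader who checks the calculation cannot reproduce it. Second, the stated SD of 20 and the SD of about 32 implied by ±15 give different pictures of what the pilot expects. Since the pilot is meant to inform the size of a later trial, the planning SD should be unambiguous.

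**Working it through.** **Inputs, all from section 5.4.4.1:** n = 20, SD = 20 minutes, two-sided 95% level, stated half-width 15 minutes. The assumed mean of 95 minutes does not affect the half-width.

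**Attempt to reproduce the stated figure.** Half-width = t(0.975, n−1) × SD/√n.

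- Standard error: 20/√20 = 4.472 minutes.
- With t on 19 degrees of freedom: 2.093 × 4.472 = 9.36 minutes, an interval of about 85.6 to 104.4 around a mean of 95.
- With the normal quantile: 1.960 × 4.472 = 8.77 minutes.
- Ratio of stated to computed: 15/9.36 = 1.60.

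The stated figure is not reproduced.

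**What ±15 would correspond to, changing one input at a time:**

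- Confidence level, at n = 20 and SD 20: 15/4.472 = 3.354 standard errors, which on 19 degrees of freedom is a 99.7% interval.
- SD, at n = 20 and 95%: 15 × √20/2.093 = 32.05 minutes.
- Number of patients, at SD 20 and 95%: n = 10 gives 2.262 × 20/√10 = 14.3; n = 9 gives 2.306 × 20/√9 = 15.4. So 10 by the plug-in formula.

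**Other readings, at n = 20 and SD 20 unless noted:**

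| Reading | Result (minutes) |
|---|---|
| One-sided 95% | 7.7 |
| 99% interval | 12.8 |
| Full width of the 95% interval | 18.7 (t), 17.5 (z) |
| Half-width not exceeded with 80 / 90 / 95 / 99% probability | 10.5 / 11.2 / 11.8 / 12.9 |
| Upper 80 / 90 / 95 / 97.5% limit for the SD put into the formula | 11.0 / 12.0 / 12.8 / 13.7 |
| Difference of two means, 20 v 20 | 12.8 |
| Difference of two means, 10 v 10 | 18.8 |

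None gives 15.

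**Loss from analysis.** Plug-in half-widths at SD 20 with fewer patients analysed are 9.9 at n = 18, 10.7 at n = 16 and 12.7 at n = 12. Starting from 10 patients, reaching 20 by attrition alone needs 1 − 10/20 = 50% loss.

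**Is 20 enough for ±15?** With normal data and all 20 analysed, the observed half-width is within 15 when the observed SD is at most 32.05. The probability of that is P(χ² on 19 df ≤ 19 × 32.05²/SD²):

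| True SD (minutes) | P(half-width ≤ 15) |
|---|---|
| 20 | 0.9998 |
| 25.4 | 0.95 |
| 28 | 0.84 |
| 32 | 0.55 |

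**The case against.** The strongest reply is that the sentence is true as written. It claims sufficiency, not equality, and at SD 20 the half-width is all but certain to fall within 15. It does not say that 20 is the smallest adequate number.

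The figure of 10 patients also overstates the slack for planning. At n = 10 and SD 20 the observed half-width is within 15 only about 64% of the time. Requiring 80, 90, 95 or 99% assurance takes 12, 14, 15 or 17 patients. From 17, an assumed 15% loss gives 17/0.85 = 20; from 15, an assumed 25% loss gives 15/0.75 = 20. The ceiling on enrolment, the exclusion for any deviation and the complete-data requirement make some loss plausible. A headline of ±9.4 would also promise too much if fewer than 20 are analysed. Finally, the later trial would use the SD observed in the pilot, not the planned half-width.

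Most of this stands. The statement is a valid, conservative bound, the consequence is small, and ±9.4 must be tied to 20 analysed patients. It does not supply the missing reasoning, however. The loss rates and assurance levels above are assumptions made to reach 20; the document states none of them. If such a margin was intended, the remedy is still to write it down.

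**Conclusion.** The concern holds as a matter of clarity. On its own inputs the plan's 95% half-width is ±9.4 minutes (t) or ±8.8 (z), against a stated ±15, and nothing in the document accounts for the factor of 1.6. The result assumes a one-sample interval for a mean with all 20 patients analysed; the assurance probabilities also assume normally distributed times. The discrepancy is conservative: the study is large enough for the precision it states, and no enrolment decision, test or decision rule rests on the figure. Whether an input was left out or the number is an error cannot be settled from the document.

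**What to change.** Replace the precision sentence in section 5.4.4.1 with wording such as:

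> With 20 patients in the analysis and an SD of 20 minutes, the 95% confidence interval for mean procedure time will be about ±9.4 minutes. The half-width will be within ±15 minutes if the observed SD is no more than about 32 minutes.

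Because 20 is a ceiling and sections 5.4.1 and 5.4.4.2 can only reduce the number analysed, it would help to add the figure for a plausible smaller number, for example about ±10.7 minutes with 16 analysed.

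If ±15 was meant to cover a larger SD, an expected loss from analysis or an assurance level, state that input instead, so that the number of patients, the SD and the half-width agree. The cost is one sentence, or two with the smaller-number figure. Enrolment, endpoints and procedures are unchanged.

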##### 5.4.4.2 *Analysis Populations*

###### **Safety Population**

All enrolled subjects who underwent a catheter ablation of persistent and paroxysmal atrial fibrillation procedure will be included in the safety population.

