#### 4.5 General Inclusion Criteria

Participants must meet all of the following general inclusion criteria:

1. Adult patients (age over 18 years)
2. Undergoing first left atrial ablation for the treatment of atrial fibrillation including pulmonary vein isolation
3. Undergoing catheter-based ablation procedure using radiofrequency energy
4. Patients must be able to understand and critically review the informed consent form.
5. Subjects must understand and agree to study requirements and sign a written informed consent.

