### *5.4.4.3 Safety Analysis*

All safety-related issues related to the usage of the device will be recorded and documented as **device-related AEs (ADE)**. All safety analyses will be performed on the safety population. No imputation of missing observations will be performed. The Medical Dictionary for Regulatory Activities (MedDRA) version 13.0 or later will be used to code all AEs to a system organ class (SOC) and a preferred term (PT) within the SOC.

The incidence and frequency of AEs will be summarized by system organ class and preferred term for all AEs, device-related AEs (with relationship to study devices and/or study-device-related procedure), serious device-related AEs and device-related AEs leading to study withdrawal and death. The incidence of ADEs will also be tabulated by seriousness, severity, and relationship to study devices and/or procedure.

No AEs will be recorded for study purposes that are not specifically device-related (e.g. arrhythmia recurrences) as this is not within the scope of the study.

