## 6.1 Pre-Procedure Subject Preparation/Baseline

Prior to subject participation the following steps will be completed and documented in the CRF:

1. Signed informed consent is obtained.
2. Confirmation that all inclusion criteria are met.
3. Confirmation that no exclusion criteria are present.
4. All subjects enrolled into this study will undergo and have documented the following evaluations (within two weeks prior to study unless otherwise noted) as standard of care in the Center but not related to the study:
  - a. Medical history and physical examination
  - b. Pregnancy test in female of childbearing potential
  - c. Standard of care AF ablation pre-procedure testing (CT or/and TEE)

Informed consent will be obtained by the study investigators after discussion with the patient. The study investigators will provide additional information required and requested by the patient. Any information needed for fulfilling the study requirements will be gathered prior to inclusion. Enrollment begins when the informed consent form has been executed.

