### Active Esophageal Cooling

In consented patients, the ensoETM esophageal heat transfer device will be inserted according to standard protocol during preparation for the ablation procedure, following intubation. The ensoETM is a

non-sterile multi-lumen silicone tube placed in the esophagus much like a standard orogastric tube. The ensoETM holds FDA clearance and is intended for use as a thermal regulating device intended to connect to an external heat exchanger in order to modulate and control patient temperature. The device will remain in place until the ablation procedure is completed. Patients will undergo posterior wall ablation when the ensoETM device has reached a temperature of 4-6°C for at least 2 minutes. The device will be set to neutral body temperature (no cooling) during other aspects of the procedure.

[figure not shown]

Figure 2: The esophageal heat transfer device is constructed from medical grade silicone with an outer diameter of ~12mm (36 Fr), length of 758mm, and circulating water volume of 55mL. The device is placed similarly to an orogastric tube. Distilled water circulates inside the tube (never entering the patient), directly cooling the esophageal tissue.

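### The safety population is tied to undergoing ablation rather than to device exposure, so on the plain reading a patient injured at device insertion whose case stops before ablation is missing from the device-event tables

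*Combined protocol and SAP*

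**What the plan says.** The Safety Population paragraph of section 5.4.4.2 reads: "All enrolled subjects who underwent a catheter ablation of persistent and paroxysmal atrial fibrillation procedure will be included in the safety population". It does not mention the device. Section 5.4.4.3 makes this set the basis of all safety output: "All safety analyses will be performed on the safety population". That output is a set of incidence tables: "The incidence and frequency of AEs will be summarized by system organ class and preferred term for all AEs", followed by device-related events, serious device-related events, and device-related events leading to withdrawal or death. The same section says that events not specifically related to the device are not recorded for the study.

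On timing, section 6.1 states: "Enrollment begins when the informed consent form has been executed". Section 4.1 states: "Once the patient is intubated, the esophageal heat transfer device will be placed into the esophagus according to the IFU". Section 6.2 agrees: "In consented patients, the ensoETM esophageal heat transfer device will be inserted according to standard protocol during preparation for the ablation procedure, following intubation".

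Three other places bear on the point:

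- Section 5.4.1 excludes patients with protocol deviations from the final analysis and makes no exception for safety.
- Sections 5.4.4.3, 6.7 and 8.3 require adverse device events to be documented and followed, without limiting this to the safety population.
- Section 7.1.2 likens the device risk to that of introducing an ordinary orogastric tube.

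**The concern.** A safety set should follow exposure to the thing whose safety is being described. Here that is the ensoETM, and exposure starts at insertion. The set is instead opened by a later event, the ablation. Between the two lies the step that section 7.1.2 itself treats as the source of device risk.

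The gap is not random with respect to outcome. The patient who falls into it is one in whom a device event was bad enough to stop the case. With up to 20 patients, a single such exclusion decides whether the device-event table shows an event or none. The study is also meant to inform a larger one. Section 5.4.4.3 plans a row for device-related events leading to withdrawal or death. An insertion injury that ends the case is a natural candidate for that row, yet the patient would not be eligible to be counted in it.

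**Working it through.** The plan states no figure for safety that could be reproduced: it gives no expected rate of insertion injury, no expected rate of abandoned cases and no precision target for device events. The check is therefore a reading of the sections in sequence, followed by an illustration.

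**Step 1. Follow one patient through the plan.**

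| Stage | Source | Status |
|---|---|---|
| Consent signed | 6.1 | Enrolled |
| Intubated, ensoETM inserted | 4.1, 6.2 | Exposed to the device |
| Insertion injury, case stopped | assumed | Adverse device event, documented and followed (5.4.4.3, 6.7, 8.3) |
| Ablation | not reached | Condition of the safety population not met (5.4.4.2) |
| Safety tables | 5.4.4.3 | Not counted in numerator or denominator |

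No section defines a device-exposed set or adds this patient back.

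**Step 2. Direction of the effect.** Let n patients have insertion attempted, let k of them have a device event that stops the case before ablation, and let x of the remaining n − k have some device event. The current definition tabulates x/(n − k). A set based on attempted insertion tabulates (x + k)/n. The second is at least as large as the first when (x + k)(n − k) ≥ xn, which reduces to k(n − k − x) ≥ 0. This always holds, because x cannot exceed n − k. Leaving these patients out can therefore lower the tabulated rate but never raise it.

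**Step 3. Size, as an illustration.** Inputs: n = 20 (the maximum in the synopsis), with insertion attempted in all 20; x = 0; k = 1 or 2. The values of x and k are assumptions. The intervals are exact (Clopper-Pearson) 95% limits.

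- 0/19: upper limit 1 − 0.025^(1/19) = 17.6%.
- 1/20: lower limit 1 − 0.975^(1/20) = 0.1%; upper limit, the 97.5% point of Beta(2, 19), = 24.9%.
- 0/18: upper limit 1 − 0.025^(1/18) = 18.5%.
- 2/20: lower limit, the 2.5% point of Beta(2, 19), = 1.2%; upper limit, the 97.5% point of Beta(3, 18), = 31.7%.

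| Assumed k | Current definition | Attempted insertion |
|---|---|---|
| 1 | 0/19 = 0% (0 to 17.6%) | 1/20 = 5% (0.1 to 24.9%) |
| 2 | 0/18 = 0% (0 to 18.5%) | 2/20 = 10% (1.2 to 31.7%) |

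Section 5.4.4.3 does not mention confidence intervals. They are shown here only to indicate how much one patient matters.

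**The case against.** **The wording can be read more loosely.** The safety set asks that a patient underwent an ablation procedure, while the evaluable set uses a tighter verb: "All enrolled subjects who have received catheter ablation of persistent and paroxysmal atrial fibrillation". The looser wording might cover a case begun and then abandoned. The secondary endpoint of total procedure time starts at entry to the EP lab, and the schedule in section 6 collects device events under the index procedure. Against this, sections 5.2 and 6.2 place insertion before, or in preparation for, the ablation procedure, and the plan never says when a procedure counts as undergone. This objection stands in part: the exclusion is the plain reading, not the only one. The ambiguity is itself a reason to settle the text.

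**The event would not disappear.** A reader might infer that it goes unreported. The documents do not support that. Adverse device events are documented and followed regardless of population, section 5.4.4 plans patient listings, and section 6.7 provides for an end-of-study report of serious events to the Ethics Committee if required. This objection stands. The loss is from the incidence tables, not from the record.

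**Other stopped cases.** A reader might extend the point to any anesthetic event or device failure that ends the case. An anesthetic event unrelated to the device is not recorded under any population definition (5.4.4.3). Device failures have their own reporting route (8.4), and spare devices are planned (section 9), so a failure need not end the case. The point rests on device-related insertion injury.

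**AF type.** Both population definitions name persistent and paroxysmal AF, whereas section 4.5 sets no limit on type: "Undergoing first left atrial ablation for the treatment of atrial fibrillation including pulmonary vein isolation". A reader might infer that some enrolled patients fall outside both sets. The phrase is more naturally descriptive, and nothing in the documents suggests that another type would be enrolled. This is a matter of wording only.

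**Low stakes.** Safety is neither the primary nor a listed secondary endpoint, no decision rule uses the rate, and such cases may be rare. That limits the weight of the point but does not remove it.

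**Conclusion.** The concern holds in a limited form. The safety population is anchored to ablation rather than to device exposure. On the plain reading, an enrolled patient with a device-related insertion injury that stops the case before ablation is therefore left out of the planned device-event tables. The exclusion depends on outcome and can only lower the tabulated rate.

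Its size depends on an event for which the documents give no rate. If no such case occurs, nothing changes. If one occurs among 20 with no other device event, the table shows none instead of one in 20. The conclusion assumes that undergoing a catheter ablation procedure requires the ablation to have begun. It is a correction worth making before data exist, not a flaw in the efficiency analysis.

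**What to change.** 1. In section 5.4.4.2, define the safety population as all enrolled subjects in whom ensoETM insertion was attempted, whether or not ablation was started or completed.
2. State in section 5.4.1 or 5.4.4.3 that the exclusion of patients with deviations does not apply to the safety analyses. Without this, an abandoned case logged as a deviation could be removed by that second route even after the population is redefined.
3. As a minor alignment with section 4.5, refer simply to atrial fibrillation in the evaluable definition and wherever the safety definition still names AF type.

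The cost is a few sentences of protocol text, with no added patients or assessments. The downside is that the safety denominator may include a patient with no ablation data. That patient is outside the efficiency analysis anyway, because the evaluable population requires complete ablation and timing data.

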## **Evaluable Population**

All enrolled subjects who have received catheter ablation of persistent and paroxysmal atrial fibrillation with complete ablation data and procedural timing will be included in the evaluable population.

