#### 5.2 Informed Consent

This study will require subjects to have the ensoETM inserted intra-orally prior to the ablation procedure. As the ensoETM is not routinely used at this Center, detailed information regarding risks are included in the Informed Consent Form presented to subjects enrolling in the study.

This study will require that the operating physician carry out the standard of care for AF ablation. Ultimately, the number and location of ablation lesions and determination of whether to end the procedure will be at the discretion of the operating physician and will be based on the Center's standards as used in recent years. Subjects will be required to sign an Informed Consent Form detailing the potential risks and benefits of their study participation. A study subject can withdraw consent at any time, and for any reason. All patients included will also sign a separate informed consent for AF ablation procedure as standard in the Center.

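### The evaluable-population definition and the deviation-exclusion rule give different primary analysis sets; applying the exclusion as written removes failed-device cases from the efficiency estimate

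*Combined protocol and SAP*

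**What the plan says.** Protocol 5.4.4.2 makes evaluable, without further condition, "All enrolled subjects who have received catheter ablation of persistent and paroxysmal atrial fibrillation with complete ablation data and procedural timing". The Safety Population in the same section likewise has no device condition: "All enrolled subjects who underwent a catheter ablation of persistent and paroxysmal atrial fibrillation procedure will be included in the safety population". The Primary Endpoint Analysis paragraph defines the time interval but does not say in whom it is analysed.

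Enrolment comes early. Section 6.1: "Enrollment begins when the informed consent form has been executed". Insertion comes later. Section 4.1: "Once the patient is intubated, the esophageal heat transfer device will be placed into the esophagus according to the IFU". Between the two, section 5.2 applies: "A study subject can withdraw consent at any time, and for any reason". The same section says that a separate Center consent covers the ablation itself.

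Cooling is a condition of the key step. Section 4.1 says that posterior wall ablation "will only be performed when the ensoETM has reached a temperature of 4-6°C for at least 2 minutes". Section 5.4.3 counts any variance from the plan as a deviation, and section 5.4.1 takes patients with deviations out of the final analysis while still summarising the deviations in reports. Section 8.4 has device failures recorded on the case report form and reported to the company, but gives no analysis rule for them.

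**The concern.** The trial estimates procedure time with active cooling, and section 3.2 sets that time against historical controls treated with temperature monitoring. The analysis set therefore has to settle two things: whether patients who never received the device count, and whether patients in whom the device was tried and failed count. The plan answers neither consistently.

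A never-exposed patient in the set contributes comparator-like treatment to the intervention mean and pulls the contrast towards zero. A failed placement or mid-case failure is different: it is part of what using the device involves. If such cases tend to run longer, removing them afterwards makes the device look faster than it was in practice. The historical controls face no matching exclusion for device failure. The resulting mean and SD also feed the sample size of the next trial (5.4.4.1).

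**Working it through.** **1. The two rules applied to the same patients**

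| Case | 5.4.4.2 read alone | 5.4.1 with 5.4.3 |
|---|---|---|
| Consents, withdraws before insertion, is ablated under the Center's own consent, timing available | Meets the wording; no rule on the data of withdrawn subjects | Withdrawal is a right under 5.2 and not clearly a deviation, so exclusion is not assured |
| Device cannot be placed, ablation goes ahead | Included | Departs from 4.1, so excluded |
| Device fails, posterior ablation finished uncooled | Included | Departs from 4.1, so excluded |

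Two analysts could form different primary sets from the same 20 patients, each following the text.

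**2. The plan's precision figure, as a yardstick**

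Inputs from 5.4.4.1: n = 20, SD = 20 minutes, stated 95% interval of ±15 minutes.

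Half-width = t(0.975, 19) × SD/√n = 2.093 × 20/√20 = 9.36 minutes (8.77 with the normal quantile).

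The stated ±15 is not reproduced. It holds only as an upper bound. This point does not depend on it, and 9.36 is used below for scale.

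**3. Never-exposed cases kept in the mean**

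Let k of 20 be fully uncooled, with times differing from cooled times by D minutes. The documents give neither value; D = 10 to 30 is assumed.

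Shift in mean = k × D/20; dilution of the contrast = k/20.

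| k | Shift, D = 10 | Shift, D = 30 | Dilution |
|---|---|---|---|
| 1 | 0.5 min | 1.5 min | 5% |
| 2 | 1.0 min | 3.0 min | 10% |
| 3 | 1.5 min | 4.5 min | 15% |

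**4. Failure cases dropped from the mean**

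Let k of 20 attempted cases run E minutes longer than the rest, which average m. The mean of all attempted cases is [(20 − k)m + k(m + E)]/20 = m + kE/20. After exclusion it is m. The reported mean is therefore too short by kE/20. With E also assumed at 10 to 30 minutes, this is again 0.5 to 1.5 minutes per case. E is unknown: a failure part-way through is partly cooled and could run longer than either pure strategy. If failed cases ran shorter, the sign would reverse.

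**5. Precision if patients leave the set**

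The same half-width formula with SD 20 gives 9.64 minutes at n = 19, 9.95 at n = 18 and 10.66 at n = 16. All are inside ±15.

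**The case against.** The strongest reply is that 5.4.1 already settles the matter. A reader might infer from 5.4.4.2 that a case finished uncooled after a device failure is counted as a cooled procedure time. The documents do not support that: such a case departs from 4.1, is a deviation under 5.4.3, and is excluded under 5.4.1. This stands. For device failures the problem is the exclusion itself, together with the absence of any link between the two rules.

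Nor would failures go unrecorded. Set point and timing are annotated in the mapping software, failures go on the case report form, and deviations are summarised in the report. Failures leave the mean but not the record. Section 9 also supplies about 10% additional devices, partly for replacement, so a failure need not lead to an uncooled case.

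The withdrawal example is an inference. No text describes withdrawing from the device alone while data collection continues, or says that later data are analysed. Inclusion is possible on the literal wording, not stated.

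A reader might also see a contradiction between 4.1 and 5.2, where "the number and location of ablation lesions and determination of whether to end the procedure will be at the discretion of the operating physician". There is none in terms: one sets a condition on posterior lesions, the other leaves their number and location and the end of the case to the operator, and both can be followed. The documents are silent on how they apply together once the device has failed.

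Finally, the shifts are small against the sampling error. That is true, but they are bias, which the interval does not show.

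**Conclusion.** The point holds as an unreconciled analysis set. One rule includes all enrolled and ablated subjects with complete data, the other excludes everyone with a deviation, and the primary analysis names neither. Following the exclusion as written removes the device's own failures and failed placements after the fact, which can favour the device against historical controls.

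The size is modest: 0.5 to 1.5 minutes per case among 20, against a half-width of about 9.4 minutes. This rests on assumed differences of 10 to 30 minutes and on the plan's SD of 20. The documents give no rate of failure, withdrawal or failed placement, so the number of affected patients may be zero. The change is worth making because it is cheap and should be settled before the data are seen; the finding does not undermine the pilot.

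**What to change.** Amend 5.4.1 and 5.4.4.2 together; changing the population definition alone would leave the exclusion rule in force.

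- Define the primary set as all patients in whom ensoETM insertion was attempted under active consent and ablation was started, and name it in the Primary Endpoint Analysis paragraph.
- Keep failed placements, device failures and switched cases in the primary mean, flagged with the time of the switch.
- List withdrawn and never-exposed patients separately, outside the mean.
- Add one supportive analysis limited to patients whose posterior lesions were all delivered at the protocol water temperature, using the set-point and timing record from 5.4.1.
- State how 4.1 and 5.2 apply together after a device failure. That is for the trial team to settle; no clinical rule is proposed here.

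The cost is wording in three places, one flag, one listing and one supportive table, drawn largely from data that 5.4.1 and 8.4 already have recorded. The downside is that a never-exposed patient leaves the count, so n may fall by one or two; at n = 18 the half-width would be 9.95 minutes.
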